5.5 Strategies for Recruitment and Retention

Children attending Early Childhood Education programs in Pohnpei State will be enrolled. In 2015 there were 9 centers enrolling 597 children. Maximum enrollment will be children. We expect to be able to enroll the entire sample from Nett, Kolonia, Saladak, Awak, ESDM, Pohnpei Catholic, UCCP, Calvary Christian and St. Paul centers but will recruit from other

centers as required. Based on our previous work in Micronesian schools in the US affiliated states we expect nearly every parent to consent and thus for us to enroll the entire sample within two months (Milgrom et al., 2009; [name] et al., 2010; Milgrom et al., 2011).

The parent (or legal guardian) of the potential subject will be approached by a study assistant who will confirm eligibility of the subject. The proposed study will be explained. Written informed consent will be obtained. Up to 600 families will be enrolled.

The Micronesian islands are quite isolated and children do not change schools or move from the islands readily. We will regularly provide healthy snacks at the centers and hold end of year study parties for parents and children at the centers to reduce dropouts. Families whose children complete the first treatment visit will receive a \$35 gift card as an incentive. Families whose children complete a year in the study will receive another \$35 gift card; families whose children complete two years in the study will receive a third \$35 gift card. In addition, the children will receive a study backpack including a set of school supplies. To be more inclusive, all children in the programs will receive a free study t-shirt, irrespective of whether they are enrolled in the study. The incentive levels were determined based on advice from Department of Health. We have conducted two prospective cohort studies with a similar population in the islands. The one-year attrition rate was 1/172 (less than 1%) in one study and no child was lost to follow-up in the other study ([name] & Milgrom, 2010; Milgrom, [name] & Mancl, 2011).

5.6 Treatment Assignment Procedures

5.6.1 Subject Identification Numbers

Participants will be randomly assigned to one of the two interventions with a 1:1 allocation as per a computer-generated randomization schedule with stratification on school and with randomly permuted blocks of sizes 2 and 4. Stratification and blocking will ensure the two interventions are equally balanced within school and randomly permuted blocks sizes will ensure concealment. The study biostatistician will create the randomization lists using the “sample” function of the R statistical software (Version 3.3.0; The R Foundation for Statistical Computing, 2016).

5.6.2 Randomization Procedures

The study biostatistician will create the randomization lists using the “sample” function of the R statistical software (Version 3.3.0; The R Foundation for Statistical Computing, 2016).

The biostatistician will generate an assignment list. Individual envelopes will be prepared and the clinician will open the envelope to reveal the instruction for which coded drug (A or B) to apply. The envelopes and the drug containers

will be color coded to minimize error. In each case a second staff member will verify on site that the child received the correct coded treatment.

5.7 Masking Procedures

All study personnel except for designated personnel in the data center will be blinded to the participant treatment assignment. In order to maintain blinding, the caries scoring examinations will precede the application of test varnishes at baseline. The staff member applying these varnishes will not perform the caries scoring exams in order to eliminate examiner bias and ensure blinding to treatment assignment.

5.8 Reasons for Withdrawal

Subjects' parents or legal guardians will be advised in the written consent that they have the right to withdraw from the study at any time without prejudice, and may be withdrawn at the Principal Investigator's discretion at any time.

A subject may be withdrawn from the study for the following reasons:

Examples of non-adverse-event related reasons for withdrawal

1. Withdrawal of consent by parent/guardian
2. Principal Investigator-initiated withdrawal
3. Request of primary care physician
4. Failure to meet entry criteria (either newly developed or not previously recognized)
5. Lost to follow-up/failure to return
6. Early termination of study

Examples of adverse event-related reasons for withdrawal

1. New illness that in the opinion of the Principal Investigator warrants withdrawal
2. Death
3. Other adverse event

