5.3 Subject Exclusion Criteria

A subject who meets any of the following criteria will be excluded from participation in this study:

1. Known allergy to iodine
2. Known allergy to seafood
3. Known hypersensitivity to fluoride varnish
4. Diagnosis of thyroid disease
5. Chronic, prophylactic use of antibiotics
6. Treatment with another investigational drug or other intervention within 30 days preceding the Baseline Visit.

In the event of unique circumstances permitting waiver of any of the above eligibility criteria, documentation of such a waiver must be generated by the Principal Investigator prior to randomization into the study. Enrollment of an otherwise ineligible subject into the study without prior approval of a waiver will be considered a protocol violation.

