6.1.2 Formulation, Packaging, and Labeling

Advantage Anti-Caries Varnish. The active ingredients are 10% (w/v) Povidone Iodine CAS RN 25655-41-8 and 5% (w/v) Sodium Fluoride CAS RN 7681-49-4 in Ethanol 200 Proof. The formulation of the dosage form includes 10% Nt-2 Premium Shellac, 1% sodium phosphate, dibasic anhydrous, 0.5% ammonium phosphate, monobasic, and 1% caramel cream flavor (Bell 29.26303) as inactive ingredients. One and two-year shelf life of the varnish has been established according to Guidance for Industry Q1A(R2) Stability Testing of New Drug Substances and Products (Revision 2, November 2003).

The active control varnish will be the same fluoride varnish without iodine with an appropriate FDA approved food dye added to match the color of the test agent. There will be no difference in the treatment and control varnishes except for the povidone iodine.

The varnishes will be packaged in 12 mL multi use bottles with the following labeling.

Advantage Anti Cavity Varnish or Control Varnish

- Apply as per protocol
- For Investigational Use Only
- Drug Code A or B
- Contact: [name], [contact] (24 hours)

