6.5 Coding/Emergency Treatment Disclosure

The Principal Investigator will be given a sealed envelope containing the randomized treatment assignment code for each subject to be opened only in the event of a medical emergency.

Neither premature withdrawal from the study nor most clinical emergencies necessitate disclosure of treatment assignment. Most emergency situations can be handled by withdrawing study treatment without disclosure of treatment assignment. However, in rare circumstances under which knowledge of the drug assignment is necessary for the treatment of a serious adverse event, the Principal Investigator ([name]) must discuss the situation with the Site Director ([name]) and [name], if circumstances permit, before deciding whether or not to disclose treatment assignment. If disclosure of individual treatment assignment is undertaken, it must be made by the Principal Investigator responsible for the care of the involved subject in consultation with the Medical Monitor ([name]). The subject will be withdrawn from further exposure to study drug.

Emergency treatment disclosure is a reportable event, requiring notification to the Principal Investigator within 24 hours of the disclosure. The assigned treatment must not be revealed to other study staff or to individuals who are not involved directly in the clinical care of the subject, unless disclosure to the individual is critical to the care of the subject.

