9.4 Expected Adverse Reactions

Risks from povidone iodine include rash and swelling at the site of application. Iodine can cause thyroid gland problems.

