11.3 Statistical Analysis Plan

11.3.1 Primary Statistical Analysis.

The primary analysis will be conducted in accordance with the intention-to-treat principle, and multiple imputation procedures will be used to account for missing caries information (Schafer, 1997). For the primary outcome, incremental dental caries based on d₂₋₃mfs/DMFS, the unit of analysis will be the child and the mean dental caries increment will be compared between the two interventions separately at 1 and 2 years post baseline using a two-sample t test assuming unequal variances. This approach assumes the distribution of dental caries increment is approximately symmetrical, which is often true in high-risk caries populations. In this case, non-symmetry, log-linear regression using robust standard errors, which can accommodate count outcomes with skewed distribution, will be used to compare the caries rates between the two interventions (Hardin & Hilbe, 2003). Covariate-adjusted linear (or log-linear) regression models using robust standard errors will be used to compare dental caries increment, adjusting for baseline dental caries, stratification variables (education center and school), gender and age of the participant (Hardin and Hilbe, 2003). Analyses will be performed using R (The R Foundation for Statistical Computing, 2016; Version 3.3.0) and SAS (SAS Institute, Cary, NC, Version 9.4).

11.3.2 Analysis of Safety Data.

Adverse events (AEs) will be tabulated by treatment group, severity, and perceived relationship to investigational product. For each AE, treatment group comparisons regarding the occurrence of at least one event will be made using Fisher's exact tests. The comparisons will be repeated excluding all mild symptoms. Similar analyses will be performed after grouping AEs by body system using standard Medical Dictionary for Regulatory Activities (MedDRA) coding. Individual AEs will be listed, with particular attention paid to serious AEs.

11.3.3 Participant Disposition.

The frequency and reasons for withdrawal will be summarized by treatment group, as will the number of missed visits and missed treatment applications (compliance).

12. Source Documents and Access to Source Data/Documents

The site will maintain appropriate medical and research records for this trial, in compliance with ICH E6, Section 4.9 and regulatory and institutional requirements for the protection of confidentiality of subjects.

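### Section 5.8 allows withdrawal from the whole study, not only from varnish, so obtainable 24-month caries outcomes may be lost for treatment-related reasons despite the intention-to-treat claim

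*Combined protocol and SAP*

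**What the plan says.** Section 5.8 opens its list with "A subject may be withdrawn from the study for the following reasons". Among the reasons given as unrelated to adverse events are withdrawal initiated by the Principal Investigator and "Failure to meet entry criteria (either newly developed or not previously recognized". A second list covers new illness and other adverse events. Both lists concern leaving the study.

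The exclusion criteria in section 5.3 include "Known allergy to iodine" and "Diagnosis of thyroid disease". Section 6.1.2 says of the two products: "There will be no difference in the treatment and control varnishes except for the povidone iodine". Section 9.4 gives rash and swelling at the application site as risks of povidone iodine and adds: "Iodine can cause thyroid gland problems".

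Two other sections use a narrower idea. After emergency unblinding, section 6.5 says: "The subject will be withdrawn from further exposure to study drug". Section 9.5.2, on abnormal clinical findings, speaks of withdrawal from study treatment.

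The primary outcome is the caries increment at 24 months (section 3.2.1). Section 11.3.1 states: "The primary analysis will be conducted in accordance with the intention-to-treat principle". It assigns missing caries data to multiple imputation.

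**The concern.** Intention-to-treat needs the outcome of each randomised child wherever it can be obtained, whether or not varnish continued. Section 5.8 does not separate stopping varnish from ending follow-up. A condition that arises after randomisation, possibly because of the iodine, can therefore end outcome collection, and it could do so more often in the test arm. The value that could have been measured is then replaced by an imputed one. How well the imputed value stands in for a child who has stopped varnish depends on a model that the plan does not give.

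The loss would be largely avoidable. Section 7.3 places the visits at the child's own centre, with caries exams at visits 4 and 8 (taken here as the one-year and two-year exams). Section 5.5 expects few children to move away. Section 6.4 treats a missed dose as a protocol deviation, so incomplete treatment does not in itself end participation.

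**Working it through.** **1. The sections side by side**

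| Section | What ends | Caries exam afterwards |
|---|---|---|
| 5.8 | Study participation | None stated |
| 5.8.1 | Study participation, voluntary withdrawal | One final exam at the withdrawal visit |
| 7.5 | Study participation, any premature withdrawal | One exam at the withdrawal visit |
| 6.5 | Exposure to study drug | Not stated |
| 9.5.2 | Study treatment | Not stated |

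Two things follow. The scope of the withdrawal exam differs between 5.8.1 and 7.5. No section provides the 24-month exam once a child has left the study. A child withdrawn after visit 4 also has the visit 4 exam. Section 11.3.1 gives no imputation model, no missingness assumption, no role for the withdrawal exam and no sensitivity analysis.

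**2. The plan's own sample size**

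Inputs from section 11.2: 30% reduction, coefficient of variation 75%, two-sided 0.025, power 90%. With a constant coefficient of variation,

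n = (z for 0.0125 + z for 0.90)² × CV² × [1 + (1 − 0.30)²] / 0.30² = (2.241 + 1.282)² × 0.5625 × 1.49 / 0.09 = 115.6.

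The t-based version (standardised effect 0.463) gives 117, or 119 with the effect rounded to 0.46. The stated 120 per arm reproduces closely and is not in dispute.

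**3. Illustration of size**

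The documents give no rate for such withdrawals, so everything here is assumed. Set the control mean increment to 1 and the mean of continuing test children to 0.70. Let a fraction a of test children stop near baseline and then have mean increment r. Stopping in the control arm is ignored.

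True reduction = 1 − [0.70(1 − a) + r·a] = 0.30 − (r − 0.70)a.

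If their outcomes are imputed from continuing test children, the estimate stays at 0.30. With r = 1 (reverting to the control rate), the true reduction is 0.30(1 − a):

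- a = 1%: 0.30 × 0.99 = 29.7%
- a = 2%: 0.30 × 0.98 = 29.4%
- a = 5%: 0.30 × 0.95 = 28.5%

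If half the increment has accrued before stopping, it is 0.30(1 − a/2). At a = 5% this is 29.25%.

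These figures are not an upper bound. Control children receive fluoride varnish, while a child who stops receives neither agent, so r could exceed 1. With r = 1.2 (assumed), the true reduction is 0.30 − 0.5a, which is 27.5% at a = 5%.

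**4. Direction**

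The direction depends on the imputation model. Imputing these children at the control mean, with r = 1, returns the true value and leaves no bias. Imputing them at the control mean when the earlier benefit in fact persists (r = 0.70) gives 0.30(1 − a) against a truth of 0.30, which is bias against the test varnish.

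**5. Power**

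Section 11.2's 280 children less 15% leave 140 × 0.85 = 119 per arm, with power 90.9% by normal approximation. Losing a further 1%, 2% or 5% of the test arm gives 90.7%, 90.6% or 90.1%. The issue is possible bias, not power.

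**The case against.** Several points count against a strong version of this concern.

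- Withdrawal under 5.8 is permissive, and 9.5.2 already offers treatment-only stopping for abnormal findings. This stands. It makes the problem a conflict between sections, not a uniform rule that ends follow-up.
- Thyroid disease arising on varnish would be an adverse event under 9.3, so it may belong in the second list of 5.8 and not under entry failures. That is fair, but the second list also ends study participation, so the gap remains.
- Randomised children are not dropped. They are imputed, and the withdrawal and visit 4 exams could inform the imputation. This also stands, although an early exam does not measure a 24-month increment and the plan does not say that these exams will be used.
- Such events should be few. Section 2.2.1 calls iodine-related thyroid problems rare, section 11.2 expects very low attrition, and section 5.5 reports one-year attrition of 1/172 in one earlier study and none in the other.

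A reader might also infer three things that the documents do not support. The first is that the analysis is really an on-treatment estimate favouring the test varnish. That requires imputation from continuing test children, and 11.3.1 does not specify this. The second is that 9.4 names iodine allergy as an effect of the varnish. It names site rash, swelling and thyroid problems, so the allergy link is an inference. The third is that the 15% in 11.2 measures the exposure. It is an overall attrition allowance, not a rate of treatment-related stopping in the test arm.

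**Conclusion.** The concern holds in a limited form. As written, the plan permits study withdrawal for reasons that may be related to treatment, provides no 24-month caries exam afterwards, and conflicts with its own treatment-only wording in 6.5 and 9.5.2. That weakens the intention-to-treat analysis through loss of data that could be obtained.

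The effect is probably small. Under the assumptions of early stopping, reversion to the control rate and imputation from continuing test children, 1% to 5% stopping in the test arm gives a true reduction of 29.7% to 28.5% where 30% would be estimated. This is illustrative and neither a forecast nor a bound. The direction of bias cannot be settled from the documents. The case for change is that the remedy is cheap and removes an avoidable source of bias, not that a large distortion is expected.

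**What to change.** Reconcile sections 5.8, 5.8.1, 6.5, 7.5 and 9.5.2 so that they state:

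- Stopping varnish does not by itself end study participation.
- The scheduled visit 4 and visit 8 caries exams continue unless consent for follow-up is withdrawn, or the child has died or cannot be reached.
- The values from those exams are used in the primary analysis.
- The withdrawal exam has one consistent scope.

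In 11.3.1, reserve multiple imputation for outcomes that cannot be obtained, and state its model and missingness assumption with a sensitivity analysis.

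The decision on when to stop varnish is a clinical matter and is left as it is.

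The cost is protocol wording and a few extra exams at centres where exams already take place. The expected effect may be slightly smaller, because children who stopped varnish contribute their observed outcomes.

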5.8.1 Handling of Withdrawals

In the event of voluntary withdrawal from the study, a Premature Withdrawal (PW) Visit will be conducted to obtain a final caries exam and ensure that appropriate care under medical supervision is provided until the symptoms of any AE resolve or the subject's condition becomes stable or deemed chronic.

Reasonable effort should be made to contact any subject lost to follow up during the course of the study in order to complete study-related assessments and collect safety data.

Subjects who are withdrawn from the study will not be replaced.

5.9 Termination of Study

The study may be discontinued at the discretion of the Sponsor or the Principal Investigator if there is sufficient reasonable cause.

Circumstances that may warrant termination include, but are not limited to:

- Determination of unexpected, significant, or unacceptable risk to subjects.
- Insufficient rate of subject accrual.
- Insufficient adherence to protocol requirements.
- Data which are not sufficiently complete and/or evaluable.

Written notification, documenting the reason for study termination, will be provided to the Principal Investigator and regulatory authorities. In the event of early termination of the study, all subjects will be seen for a final visit for safety purposes. The study site will notify the Western IRB and the Pohnpei State Department of Health Services of the study termination and provide the reason(s).

6. Investigational Product

6.1 Investigational Product Description

6.1.1 Acquisition

Test and control varnishes will be obtained from Cascade Custom Chemistry, Eugene, OR

6.1.2 Formulation, Packaging, and Labeling

Advantage Anti-Caries Varnish. The active ingredients are 10% (w/v) Povidone Iodine CAS RN 25655-41-8 and 5% (w/v) Sodium Fluoride CAS RN 7681-49-4 in Ethanol 200 Proof. The formulation of the dosage form includes 10% Nt-2 Premium Shellac, 1% sodium phosphate, dibasic anhydrous, 0.5% ammonium phosphate, monobasic, and 1% caramel cream flavor (Bell 29.26303) as inactive ingredients. One and two-year shelf life of the varnish has been established according to Guidance for Industry Q1A(R2) Stability Testing of New Drug Substances and Products (Revision 2, November 2003).

The active control varnish will be the same fluoride varnish without iodine with an appropriate FDA approved food dye added to match the color of the test agent. There will be no difference in the treatment and control varnishes except for the povidone iodine.

The varnishes will be packaged in 12 mL multi use bottles with the following labeling.

Advantage Anti Cavity Varnish or Control Varnish

- Apply as per protocol
- For Investigational Use Only
- Drug Code A or B
- Contact: [name], [contact] (24 hours)

6.1.3 Product Storage and Stability

All investigational products will be kept in a secure, safe area under recommended storage conditions with access limited in the study office. Expiration or use-by dates, as applicable, for all products will be documented by staff.

6.2 Dosage, Preparation and Administration of Study Investigational Products

Advantage Anti-Cavity Varnish and Control Varnish

A maximum of 0.2 mL will be applied to the teeth with a dental brush.

Test or control varnish will be applied topically following baseline examination and at each 3 to 4-month intervals.

6.3 Accountability Procedures for the Investigational Product(s)

The Principal Investigator ([name]) and Site Director ([name]) must maintain accurate records (including dates) of all supplies received from Advantage. All treatment applications (A or B) will be recorded on a Drug Accountability Log completed by the Study Director. All remaining drug will be returned to the sponsor and documented on the Drug Disposal Log.

6.4 Assessment of Subject Compliance with Investigational Product

As test drug and control drug will be administered by the study personnel, is not anticipated that subject compliance with treatment will be an issue. In the event a dose is missed; the missed dose will be captured as a protocol deviation and documented in the source documents.

6.5 Coding/Emergency Treatment Disclosure

The Principal Investigator will be given a sealed envelope containing the randomized treatment assignment code for each subject to be opened only in the event of a medical emergency.

Neither premature withdrawal from the study nor most clinical emergencies necessitate disclosure of treatment assignment. Most emergency situations can be handled by withdrawing study treatment without disclosure of treatment assignment. However, in rare circumstances under which knowledge of the drug assignment is necessary for the treatment of a serious adverse event, the Principal Investigator ([name]) must discuss the situation with the Site Director ([name]) and [name], if circumstances permit, before deciding whether or not to disclose treatment assignment. If disclosure of individual treatment assignment is undertaken, it must be made by the Principal Investigator responsible for the care of the involved subject in consultation with the Medical Monitor ([name]). The subject will be withdrawn from further exposure to study drug.

Emergency treatment disclosure is a reportable event, requiring notification to the Principal Investigator within 24 hours of the disclosure. The assigned treatment must not be revealed to other study staff or to individuals who are not involved directly in the clinical care of the subject, unless disclosure to the individual is critical to the care of the subject.

